TITLE: A PILOT STUDY OF STEREOTACTIC BODY RADIOTHERAPY (SBRT) IN OLIGOMETASTATIC RENAL CELL CARCINOMA

Principal Investigator: [name].
Department of Radiation and Cellular Oncology
University of Chicago Medical Center
[name]
[name]
[contact]
[contact]
[contact]

Sub-Investigators:

Radiation Oncology
[name] PHD
[name]
[name]

Urology
[name]
[name]
[name]

Medical Oncology
[name]
[name]
[name]
[name]

Biostatistics
[name]

Research and Nursing Support
[name]
[name]

Funding: Internally funded through the Department of Radiation and Cellular Oncology

Sponsor: [name]./University of Chicago

Intervention: Stereotactic Body Radiotherapy to all sites of disease

Protocol Version: 2.0

Protocol Version Date: 08.05.19

STUDY SUMMARY SCHEMA

Patient population:

- Histologically or cytologically diagnosed renal cell carcinoma (any histologic subtype)
- No systemic therapy or radiation therapy within 1 month prior to enrollment
 - No prior bevacizumab
- ECOG performance score 0-2 and ≥ 3 month life expectancy
- 1-5 sites of metastatic (or recurrent) disease, each ≤ 6 cm and amenable to SBRT
 - Up to 3 brain metastases may be included

Treatment:

- 25 patients will be enrolled and treated according to protocol guidelines for SBRT
- Brain metastases must be addressed prior to enrollment
- Day1 : Begin SBRT to all involved sites, 5 fractions on non-consecutive days
- Enrollment halted if there are two grade 4 toxicities within the first 2 patients, three within the first 14 patients, or 4 within the first 25 patients

Follow-up:

- Clinical follow-up to assess CTC toxicity and disease control, monthly up to 3 months, then q3 months up to 1 year
- CT chest/abdomen/pelvis q3 months up to 1 year
- Off protocol therapy at clinician discretion but no earlier than 4 weeks after start of SBRT

Required Sample Size: 25 patients would be required

Study Center: University of Chicago Medical Center, Chicago, IL

Concept and Rationale: Patients with metastatic renal cell carcinoma (RCC) have a poor prognosis with median survival between 6-15 months, as few patients have a lasting response to cytokine therapy or targeted agent therapy. However, not all patients present with widely metastatic disease. There may be a select group of patients with “oligometastatic” disease—a limited number of metastatic lesions that can be treated with curative intent using aggressive local and systemic therapy. Randomized studies suggest a benefit of cytoreductive surgery in the setting of cytokine therapy, and retrospective series suggest an improvement in survival with metastasectomy. These studies argue that aggressive local therapy to all known sites of disease can yield benefit in the properly selected patient.

However, not all lesions are amenable to surgical resection, and surgery can be associated with significant morbidity. Stereotactic Body Radiotherapy (SBRT) is a method of treatment which directs ablative doses of radiotherapy to the target lesion while limiting radiation to surrounding structures. There is an increasing body of evidence supporting a role for SBRT in oligometastatic cancers throughout the body. A prior Phase I trial at the University of Chicago suggested that a 3-fraction regimen is tolerable in oligometastatic cancer. However, this study included a heterogeneous cohort of patients with multiple primary malignancy types; only 13% of the patients in the trial had RCC. Furthermore, variable radiation doses were prescribed to different sites, complicating the applicability of findings to the clinical setting. Conclusions are therefore more difficult to make regarding the tolerability of SBRT in RCC.

We hypothesize that 5-fraction SBRT with a more uniform dose approach (by having a preferred SBRT dose that is similar for all sites of involvement) in the management of oligometastatic RCC is feasible, not associated with excess toxicity, and can be safely delivered prior to systemic therapy. Information gathered from this study will contribute towards the development of a larger, phase II Chicago consortium study.

Primary Objective: To establish that patients can be treated with 5-fraction SBRT to all sites of metastatic disease with a low (<16%) rate of severe (grade 4) toxicity.

Secondary Objectives:

1. To determine the toxicity profile of SBRT.
2. To determine the feasibility of delivering 5-fraction SBRT per protocol based on proposed normal tissue constraints in a variety of organ sites. (i.e., the ability to treat >80% of enrolled patients according to protocol guidelines).
3. To describe treated lesion control (LeC), progression free survival (PFS), and patterns of failure.
4. To determine the feasibility of accrual and adequacy of eligibility criteria by defining the proportion of eligible cases of metastatic RCC presented at the weekly multidisciplinary genitourinary conference at the University of Chicago Medical Center.
5. To make a preliminary evaluation regarding potential biomarkers in patient serum which may be assessed in a follow-up study (e.g. genetic or immunologic biomarkers).

Study Design: This is a single-armed pilot study to estimate the rate of CTCAE v4.0 grade ≥ 4 RT-related toxicity of 5-fraction SBRT in patients with oligometastatic RCC. Eligible patients must have histologically or cytologically diagnosed RCC with 1-5 sites of metastases, including up to 3 brain metastases. Patients may present with metastatic disease, or have previously treated primary disease with metastatic recurrence. All sites of metastasis must be ≤ 6 cm, and patients with recurrent/unresected primary tumors are eligible as long as said tumor is ≤ 10 cm and there is a plan to treat the primary tumor with a local therapy. Patients may not have had any oncologic therapy within 1 month prior to enrollment, no prior history of bevacizumab, and any brain metastases must be addressed with surgery and/or radiotherapy prior to enrollment. Patients will be treated with SBRT (preferred dose 50 Gy/5 fractions) to all radiographic sites of gross disease, including the primary if it can not be addressed with non-radiotherapeutic local therapy. Patients can thereafter begin off-protocol systemic therapy per medical oncology discretion, but any therapy will occur no earlier than 2 weeks after completion of RT.

The first 10 patients enrolled on the study will be considered the "initial cohort." If ≥ 3 of these patients have a CTCAE v4.0 grade ≥ 4 RT-related toxicity, enrollment will be discontinued and the trial stopped, otherwise 5 additional patients will be accrued. Study investigators will determine whether treatment related toxicities are RT-related or non-RT-related.

Statistical Methods:

Definition of primary outcome/endpoint: RT-related grade ≥ 4 toxicity will be determined on a case-by-case basis by the study group, taking into consideration the region treated with SBRT, timing of the toxicity, and the nature of the toxicity. Toxicities will be graded as per CTCAE v4.0 criteria.

Definition of secondary outcomes/endpoints: LeC will be defined as absence of clinical or radiographic progression per RECIST criteria. PFS will be defined as progression in the treated lesion, organ in which the treated lesion is present, distant failure, or death from any cause.

Analytic plan for primary objective: Rates of RT-related grade ≥ 4 toxicity will be recorded, time to RT-related grade ≥ 4 toxicity will be recorded, and freedom from RT-related grade ≥ 4 toxicity will be determined using the Kaplan-Meier method.

Analytic plan for secondary objectives: LeC and PFS will be estimated at 1 year using the Kaplan-Meier method.

Sample size justification: A sample size of 25 patients will be needed to assess the safety and appropriateness of this method, identify the optimal candidates, and optimal SBRT fractionation/dose for different clinical scenarios.

TABLE OF CONTENTS

	Page
SCHEMA	i
1. OBJECTIVES	1
1.1 Primary Objectives	1
1.2 Secondary Objectives	1
2. BACKGROUND	1
2.1 Metastatic Renal Cell Carcinoma	1
2.2 Oligometastasis	1
2.3 Stereotactic Body Radiotherapy in Oligometastasis	2
2.4 Rationale for current study	3
2.4.1 Rationale for Secondary Objectives	4
3. PATIENT SELECTION	4
3.1 Eligibility Criteria	4
3.2 Exclusion Criteria	5
3.3 Inclusion of Women and Minorities	6
4. REGISTRATION PROCEDURES	6
4.1 Patient Recruitment	6
4.2 Patient Renumeration	6
5. TREATMENT PLAN	6
5.1 Study Design	6
5.2 Definition of Grade ≥ 4 RT-related Toxicity	6
5.3 General Concomitant Medication and Supportive Care Guidelines	7
5.4 Duration of Therapy	7
5.5 Duration of Follow Up	7
5.6 Criteria for Removal from Study	7
6. RADIATION THERAPY	7
6.1 Simulation	7
6.2 Premedications	8
6.3 Target Volumes	8
6.4 Treatment Planning	8
6.5 Dose Specifications	8
6.6 Critical Structures	9
6.7 RT Treatment	13
6.8 Radiotherapy Adverse Events	13
7. RISKS AND BENEFITS	13
7.1 Radiotherapy Adverse Events	13
8. Adverse Event Reporting	15
9. Data Safety Monitoring	16
10. STUDY CALENDAR	16
11. MEASUREMENT OF EFFECT	17
11.1 Antitumor Effect and Endpoints	17
11.2 Dosimetric description of delivery of Radiotherapy	18
12. STATISTICAL CONSIDERATIONS	19
12.1 Study Design/Endpoints	19

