5. TREATMENT PLAN

5.1 Study Design

This is a pilot study of the use of SBRT to all sites of disease for patients with oligometastatic RCC. Patients may receive off-protocol systemic therapy per medical oncologist discretion no earlier than 4 weeks after starting SBRT. While there are no restrictions on systemic therapy following SBRT, caution is advised on the use of bevacizumab given prior case reports demonstrating the possibility of heightened toxicity when this agent is used in the setting of SBRT. Limited or symptomatic recurrences can also be treated with radiation therapy (either SBRT or conventional therapy) at the clinician's discretion.

Enrollment will proceed according to a sequential toxicity monitoring schema to test the null hypothesis of a $\pi_0=5\%$ grade 4 toxicity rate against an upper acceptable boundary of a $\pi_1=20\%$ grade 4 toxicity rate. Trial enrollment will be halted if there are two grade 4 events within the first 2 patients, if there are three events within the first 14 patients, or if there are four events within the first 25 patients. The treatment will be considered successful if there are less than four events in 25 evaluable patients (<16%).

Treatment will be administered on an outpatient basis. The details of planning and administration of radiotherapy are discussed in detail in section 6. Reported adverse events and potential risks for SBRT are described in Section 8. Appropriate dose modifications for SBRT are described in Section 6. No investigational or commercial agents or therapies other than those described below may be administered with the intent to treat the patient's malignancy.

The pilot study will be considered successful if 25 patients are accrued, with less than 4 having Grade 4+ toxicity events after SBRT.

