12. STATISTICAL CONSIDERATIONS

12.1 Study Design/Endpoints

This is a pilot study of the use of 5-fraction SBRT for oligometastatic RCC. Patients enrolled in the study will be treated with SBRT to all sites of disease. Enrollment will proceed according to a sequential toxicity monitoring schema [69] to test the null hypothesis of a $\pi_0=5\%$ grade 4 toxicity rate against an upper acceptable boundary of a $\pi_1=20\%$ grade 4 toxicity rate. Trial enrollment will be halted if there are two grade 4 events within the first 2 patients, if there are three events within the first 14 patients, or if there are four events within the first 25 patients. The treatment will be considered successful if there are less than four events in 25 patients, i.e., $<16\%$ observed toxicities. This design has approximately 80% power (78.8%) to declare the treatment too toxic if the true grade 4 toxicity rate is $\pi_1=20\%$.

Patients will be followed for a total of one year after completion of the trial per protocol. Patients may be treated with off-protocol systemic therapy no earlier than 2 weeks after completion of RT. The primary endpoint is the rate of grade 4 RT-related toxicity with this treatment approach. Secondary endpoints include determining the toxicity profile of 5-fraction SBRT, determining the feasibility of 5-fraction SBRT based on normal tissue dosimetric constraints based on the organ site of involvement, describing the LeC, PFS, and patterns of failure of this approach, as well as to explore the feasibility of accrual and the adequacy of the eligibility criteria of this approach.

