12.2 Sample Size/Accrual Rate

The maximum sample size will be 25 evaluable patients according to the schema above. This sample size is needed in order to signify feasibility of this disease approach and accrual to a larger, later phase trial.

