12.4 Analysis of the Primary Endpoint

The primary endpoint is the rate of grade ≥ 4 RT-related toxicity with this treatment approach. RT-related toxicity will be recorded as specified in the study calendar (section 10). All toxicity will be determined to be RT-related or non-RT-related by the study committee.

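### The synopsis stopping rule (3 of the first 10, then 5 more patients) contradicts the 2/2, 3/14, 4/25 boundary and the 25-patient maximum, and the sections count different events

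*Combined protocol and SAP*

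**What the plan says.** The document gives two accrual and stopping rules.

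- **Synopsis, Study Design.** The first 10 patients form an initial cohort. If 3 or more of them have a CTCAE v4.0 toxicity of grade 4 or higher that is RT-related, "enrollment will be discontinued and the trial stopped, otherwise 5 additional patients will be accrued". The total of 10 + 5 = 15 is implied, not printed. No threshold is given for patients 11 to 15.
- **Schema, and sections 5.1 and 12.1.** The schema reads "Enrollment halted if there are two grade 4 toxicities within the first 2 patients, three within the first 14 patients", followed by a limit of 4 in 25. Section 12.1 opens the same boundary with "Trial enrollment will be halted if there are two grade 4 events within the first 2 patients" and adds "This design has approximately 80% power (78.8%) to declare the treatment too toxic" at a true rate of 20%. Success is fewer than four events in 25 patients.

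Section 12.2 states "The maximum sample size will be 25 evaluable patients according to the schema above". The synopsis itself, under Sample size justification, says "A sample size of 25 patients will be needed to assess the safety and appropriateness of this method".

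The event counted also changes from place to place:

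| Place | Event |
|---|---|
| Synopsis Study Design rule and primary-outcome definition; section 12.4 | grade 4 or higher, RT-related |
| Synopsis Primary Objective; section 1.1 | grade 4, no attribution stated |
| Boundary in the schema, 5.1 and 12.1 | grade 4, no attribution stated |
| Closing success statement in 5.1 | "with less than 4 having Grade 4+ toxicity events after SBRT" |
| Endpoint sentence in 12.1 | grade 4, RT-related |

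Section 12.4 is explicit: "The primary endpoint is the rate of grade ≥ 4 RT-related toxicity with this treatment approach".

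**The concern.** The primary objective is safety, so the stopping rule is the trial's main decision rule. Staff working from different sections would act differently at identifiable points.

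- After 2 events in the first 2 patients, the boundary halts and the synopsis rule continues.
- After a third event in patients 11 to 14, the boundary halts and the synopsis rule continues to 15.
- At patient 15 with the boundary uncrossed, the synopsis ends accrual while sections 5.1 and 12.1 keep enrolling. A trial that ends at 15 cannot meet a success criterion that requires 25 patients.

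The event wording adds a second ambiguity. Read literally, a count of grade 4 events leaves out grade 5 and does not require attribution to radiotherapy. It would then not be the primary-endpoint event of section 12.4.

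**Working it through.** **Inputs.** Boundary limits 2/2, 3/14 and 4/25, null rate 5%, unacceptable rate 20% and stated power 78.8% come from section 12.1. The synopsis limit of 3 in 10 and the 5 further patients come from the synopsis Study Design paragraph. The 15% rate is added as an intermediate value. Each patient is taken as one independent yes/no outcome with probability p, q = 1 − p, and X_n is the number of events in n patients. Both rules are assumed to count the same event.

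**1. The plan's own figure.** The boundary has halted by patient 25 if the total reaches 4, or if it was crossed earlier and the total stayed below 4:

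P(halt by 25) = P(X_25 ≥ 4) + P(X_14 = 3)·q^11 + p²·q^12·(q^11 + 11·p·q^10)

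- At p = 0.20: 0.7660 + 0.0215 + 0.0009 = **0.7884**. The stated 78.8% reproduces.
- At p = 0.05: 0.0341 + 0.0147 + 0.0012 = **0.0500**. The document does not state this figure.

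**2. Boundary by patients 10 and 14.** A halt needs three events by then, or two in the first two patients with none after:

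- P(halt by 10) = P(X_10 ≥ 3) + p²·q^8. At 0.20: 0.3222 + 0.0067 = 0.3289. At 0.05: 0.0115 + 0.0017 = 0.0132.
- P(halt by 14) = P(X_14 ≥ 3) + p²·q^12. At 0.20: 0.5519 + 0.0027 = 0.5547 (from unrounded terms). At 0.05: 0.0301 + 0.0014 = 0.0314 (from unrounded terms).

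A trial still running after patient 14 has at most 2 events, so it cannot reach 4 at patient 15. The value by 15 therefore equals the value by 14.

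**3. Synopsis rule.** P(stop) = P(X_10 ≥ 3).

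**4. Where the rules part.** Three events in the first 10 are also three in the first 14, so every synopsis stop is also a boundary stop. The chance that the boundary has halted by 15 while the synopsis rule continues is therefore a subtraction.

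| True rate | Synopsis stops | Boundary halted by 10 | Boundary halted by 15 | Boundary halted by 15, synopsis continues | Boundary uncrossed at 15 |
|---|---|---|---|---|---|
| 5% | 0.0115 | 0.0132 | 0.0314 | 0.0199 | 0.9686 |
| 15% | 0.1798 | 0.1859 | 0.3553 | 0.1755 | 0.6447 |
| 20% | 0.3222 | 0.3289 | 0.5547 | 0.2325 | 0.4453 |

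Enumerating all 2^15 outcome sequences at 5% and 20% gives the same divergence figures and a probability of 0 for the reverse case (synopsis stops, boundary does not).

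**5. Trials uncrossed at 15.** At 20%, the 0.4453 splits into 0.7884 − 0.5547 = 0.2337 that cross during patients 16 to 25 and 1 − 0.7884 = 0.2116 that complete 25 uncrossed. In all of them the boundary text continues past 15 and the synopsis does not.

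**6. Could the 78.8% belong to the synopsis rule?** As written, that rule stops with probability 32.2% at 20%. No final threshold is printed. If one is assumed in addition to the stop at 10, the figure is 41.8% for 4 or more of 15, or 60.2% for 3 or more of 15 (the under-16% limit applied to 15 patients). None of these is near 78.8%.

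**The case against.** The best reply is that the document points clearly to the boundary. It appears three times, it alone carries a power statement, section 12.2 ties the 25-patient maximum to it, and the synopsis's own sample-size paragraph says 25. The Study Design paragraph is an isolated outlier. A team following section 12.1 would miss no synopsis stop, and the two rules differ by less than one percentage point through patient 10. Discretionary action on late toxicity (5.2) and weekly safety review (section 9) also remain.

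All of that is correct, and it makes the repair easy. It does not settle the conflict: there is no precedence clause, the outlier is current text in a part of the document that readers may use on its own, and neither discretion nor weekly review sets a number.

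On the event, section 5.2 follows the 5.1 boundary directly, its heading names grade 4 or higher and RT-related, and it sends attribution to a committee. Leaving out grade 5 is therefore a strained reading. That is fair, and it makes the event wording the lesser part of this point. Even so, the boundary sentences do not refer to 5.2, and section 12.1 names its endpoint without the words or higher.

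A last caution also stands. The 5% and 20% rates are stated for grade 4 toxicity, and the boundary speaks of events rather than patients. The 78.8% carries over to a harmonised event only if those rates still apply and each patient counts once.

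**Conclusion.** The concern holds and must be fixed. Version 2.0 contains two incompatible rules for stopping and ending accrual. If the true rate is 20%, there is a 23.3% chance that the synopsis rule continues in a trial the boundary has halted by patient 15 (17.6% at 15%, 2.0% at 5%). If the true rate is 5%, there is a 96.9% chance that the trial reaches patient 15 with the boundary uncrossed, where the texts disagree on whether to go on; at 20% this is 44.5%. The stated power is right for the 25-patient boundary and does not describe the synopsis rule.

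These figures assume independent patients, one yes/no outcome each, and the same event under both rules. The inconsistent event definition is a secondary fault, but it bears on the same decision.

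**What to change.** 1. The sponsor confirms which rule governs. Section 12.1 is the only one with a stated power, sample size and success criterion, so the natural course is to align the synopsis Study Design paragraph with it and delete the 10 + 5 scheme.
2. State one stopping rule, one maximum sample size and one success criterion, worded identically in the schema, synopsis, 5.1, 12.1 and 12.2.
3. Use one event definition in the schema, the synopsis (including its Primary Objective), 1.1, 5.1, 12.1 and 12.4, with a cross-reference to 5.2, so that the boundary counts the primary-endpoint event: grade 4 or higher, RT-related. Say that the count is of patients with at least one such event.
4. Confirm that the 5% and 20% rates are meant for that event. Requiring attribution narrows what the boundary counts, and the sponsor should accept this knowingly.

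The cost is one rewritten synopsis paragraph and short wording edits elsewhere. No extra patients are needed. If the section 12.1 boundary is confirmed and the rates in step 4 stand, the 78.8% needs no recalculation.

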2. BACKGROUND

2.1 Metastatic Renal Cell Carcinoma

Between 20-33% of patients with renal cell carcinoma (RCC) present with metastatic disease, and of patients with initially limited disease who undergo radical nephrectomy, approximately 25% will ultimately develop metastases [1, 2]. Most patients receive systemic therapy with cytokine therapy or molecularly targeted agents blocking the Vascular Endothelial Growth Factor (VEGF) pathway or mammalian target of rapamycin (MTOR). Despite these interventions, the response rate to systemic therapy is low, with 5-20% responding to cytokine agents and approximately 30-50% to small molecule receptor tyrosine-kinase VEGF inhibitors such as sunitinib and pazopanib [3-8]. Responses are generally of short duration and the median overall survival is typically between 6-15 months [8].

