11.1.5 Endpoint Definitions

Duration of treated lesion control

Duration of time from start of treatment to the time of local progression at each treated lesion. Local progression is defined as any progressive disease as judged by RECIST criteria of treated lesions

Organ-specific control

Duration of time from start of treatment to the time of development of a new lesion on imaging within an organ in which a lesion was treated with SBRT.

Progression-free survival

Duration of time from start of treatment to time of progression. Progression is defined as any new sites of disease on imaging or any progressive disease by RECIST criteria at initially treated sites of disease (within 80% isodose line).

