12.5 Analysis of Secondary Endpoints

The secondary endpoints of this study include determining the toxicity profile, LeC, and patterns of failure of this approach, as well as the feasibility of a 5-fraction SBRT regimen based on normal tissue dose constraint and treatment goals, and the feasibility of accrual to an oligometastasis trial in RCC and adequacy of the eligibility criteria.

A database will be created that is HIPAA compliant to store the information to perform analyses. A unique study number will be assigned to each patient that will be used for all analyses. Variables will be defined as described in section 11. The results of analyses will be described but no formal statistical analysis will be performed.

Grade ≥ 4 RT-related toxicities will be recorded in database and are described as in section 5.2. The ultimate allocation of a toxicity as RT-related or non-RT-related will be decided by the study committee. Toxicities of interest that occur within the 3-12 month time frame after RT start will be documented and analyzed using descriptive statistics.

The durations of treated lesion control, organ-specific control, distant metastasis free survival, progression-free, overall and cause specific survival as defined in section 11.1.5 will be calculated for each patient. Descriptive statistics will be used to estimate these secondary endpoints using the Kaplan-Meier method (secondary aims 1.2.1, 1.2.3).

The radiotherapy doses for each treated site will be recorded. The doses to the

corresponding normal tissues will also be recorded. The maximum dose to each site while staying within dose constraints will be described. The dose to each lesion will also be compared to the local control of the corresponding lesion and described.

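### Kaplan-Meier is planned for grade ≥4 RT-related toxicity and lesion control with no rule for deaths; if deaths are censored, the descriptive failure estimates are too high, but the decision rule is unaffected

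*Combined protocol and SAP*

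**What the plan says.** For the primary objective, the analytic plan in the synopsis (Statistical Methods) records rates and times of RT-related grade ≥4 toxicity and adds that "freedom from RT-related grade ≥ 4 toxicity will be determined using the Kaplan-Meier method". For the secondary objectives it says that "LeC and PFS will be estimated at 1 year using the Kaplan-Meier method". Section 12.5 lists treated lesion control, organ-specific control and several survival durations, and states: "Descriptive statistics will be used to estimate these secondary endpoints using the Kaplan-Meier method". A Kaplan-Meier curve for freedom from toxicity is named explicitly only in the synopsis; section 12.4 does not mention the method.

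The event definitions matter here. Toxicity must be judged RT-related, so a death from another cause is not an event. In the synopsis, "LeC will be defined as absence of clinical or radiographic progression per RECIST criteria". Section 11.1.5 gives the matching duration as "Duration of time from start of treatment to the time of local progression at each treated lesion". Neither counts death. PFS in the synopsis does, since its events include "distant failure, or death from any cause"; PFS in section 11.1.5 does not mention death.

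No section gives a censoring rule for deaths, a cumulative incidence estimator or any other competing-risk method.

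On prognosis, section 2.1 says that "the median overall survival is typically between 6-15 months", which describes metastatic RCC in general. Section 2.3 cites an overall survival of 32 months in a prospective phase II study of SBRT in RCC.

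**The concern.** A patient who dies of another cause can no longer have RT toxicity or progression in a treated lesion. Kaplan-Meier with such deaths censored treats these patients as if they stayed at risk like the survivors. It therefore estimates a failure probability in a setting where nobody dies first. As a statement of how many patients or lesions actually fail by a given time, 1-KM is too high whenever deaths precede events.

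What is at stake is the descriptive output. Section 2.4 says that the pilot is to support sample size calculations for later trials. A toxicity or lesion-failure rate taken from 1-KM would carry the excess forward. The report could also show a curve that sits oddly beside the crude proportion on which success is judged.

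**Working it through.** **1. The plan's own figure.** Section 12.1 states 78.8% power at a true grade 4 rate of 20%, with a boundary of 2 events in 2 patients, 3 in 14 and 4 in 25. An exact binomial recursion over 25 patients gives 0.7884, so the figure reproduces. The crossing probability at 5% is 0.050. Neither number uses Kaplan-Meier.

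**2. Inputs for the bias.**
- Median survival of 6 and 15 months: synopsis and section 2.1, metastatic RCC in general.
- Survival of 32 months: section 2.3, read here as a median, which the text does not say.
- A 1-KM of 16%: the limit in the primary objective, used as a reference value.
- A lesion failure of 10%: illustrative, and inside the 2-13% implied by the local control of 87-98% cited in section 2.3.
- Horizon of 12 months: follow-up in section 5.5. The toxicity sentence itself names no time point; one year is attached only to LeC and PFS.

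**3. Formulas** (independent constant hazards, an assumption):
- event hazard h = -ln(1 - F)/T, where F is 1-KM at time T
- death hazard d = ln 2 / median survival
- cumulative incidence CIF = h/(h + d) × [1 - exp(-T(h + d))]

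**4. Worked case.** With F = 0.16 and T = 12, h = 0.1744/12 = 0.01453 per month. At a 32-month median, d = 0.6931/32 = 0.02166. Then CIF = 0.01453/0.03619 × [1 - exp(-0.4343)] = 0.4015 × 0.3523 = 0.141.

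**5. Results.**

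| Median survival | 1-KM 16%, constant hazard to 12 months | 1-KM 16%, all toxicity in first 3 months (T = 3) | Lesion 1-KM 10%, 12 months |
|---|---|---|---|
| 32 months | 14.1% | 15.5% | 8.8% |
| 15 months | 12.4% | 15.0% | 7.7% |
| 6 months | 8.8% | 13.6% | 5.5% |

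For toxicity the excess is 1.9, 3.6 and 7.2 points with a constant hazard, and 0.5, 1.0 and 2.4 points if all toxicity is early. For lesion failure it is 1.2, 2.3 and 4.5 points.

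**6. Scale.** The binomial standard error at 16% with 25 patients is √(0.16 × 0.84/25) = 7.3 points. Every excess for toxicity is below that, most of them well below.

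**7. Curve against count.** The worst result that still passes is 3/25 = 12%. A cumulative incidence of 12% corresponds to a 12-month 1-KM of 13.6%, 15.5% and 21.6% at medians of 32, 15 and 6 months. The expected curve passes 16% only if median survival is below about 13.3 months. In a single dataset it can happen sooner: three events with 25, 17 and 13 patients still at risk give 1 - (24/25)(16/17)(12/13) = 16.6%.

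**The case against.** The strongest reply is that nothing is decided by Kaplan-Meier. Sections 5.1 and 12.1 define stopping and success by counts, and section 12.4 calls the primary endpoint a rate. This stands. A reader might infer from the synopsis that the primary safety conclusion is biased, or that a count below 16% and a curve above 16% would leave the result undecided. The documents support neither reading: the count governs.

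Second, the 6-15 month range is not this trial's population. A reader might take the 6-month column as the expected bias, but sections 2.2 and 2.3 argue that selected oligometastatic patients do better, and at 32 months the excess is about 0.5 to 2 points. This stands too, with the caveat that section 3.1 admits ECOG 2, treated brain metastases and a life expectancy of only 3 months, so early deaths cannot be ruled out.

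Third, censoring at death is inferred, since no rule is written. That is correct. The missing rule is part of the problem, and censoring is what standard Kaplan-Meier does when death is not an event. A fatal RT-related toxicity would count as grade ≥4, so only deaths without the event compete.

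Fourth, the choice of estimand is partly one of preference, the secondary analyses are declared descriptive, and for toxicity the bias errs toward overstating harm. Cumulative incidence also has a weakness of its own: it falls when early mortality is high, so on its own it could make the treatment look safer. This argues for reporting it beside survival. It does not justify leaving the handling of deaths unstated.

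**Conclusion.** The point holds as a fault in the descriptive estimates. Kaplan-Meier is named for two endpoints in which death without the event is a competing risk, and the handling of deaths is not stated. If deaths are censored, 1-KM overstates the proportion actually affected. At the survival cited for the prospective SBRT study the excess on 16% is about 2 points, or 0.5 if toxicity is early; it reaches 7.2 points only at the lowest survival quoted for metastatic RCC in general. These sizes rest on exponential survival, independent constant hazards, 32 months read as a median, and assumed toxicity timing. The stopping boundary, the success rule and the stated power are sound in this respect. The bias is systematic and cheap to avoid, and matters mainly because the estimates are to inform the next trial.

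**What to change.** - In the synopsis and section 12.5, state how deaths are handled. Estimate RT-related grade ≥4 toxicity and treated lesion failure by cumulative incidence (Aalen-Johansen), with death without the event as a competing event. Treat organ-specific control, as defined in section 11.1.5, the same way.
- State the time point for the toxicity estimate.
- Report these estimates beside the crude n/25, named as the decision quantity, and beside overall survival.
- Keep Kaplan-Meier for endpoints that include death.
- Reconcile PFS in section 11.1.5, which omits death, with the synopsis, which includes it. Under the section 11.1.5 wording the same problem would reach PFS.

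The cost is a few sentences and a standard routine. Section 5.6 already requires the reason and date of removal, with death among the reasons, and section 12.5 already plans overall survival. The one small downside is that cumulative incidence falls when early mortality is high, so it must be read with survival.
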